### Approvals:

| Site                                | Sponsor   |
|-------------------------------------|---|
| Principal Investigator
Signature | 
[name],
VP Global Regulatory Affairs and CRO
InSightec |

**A Long-term Observational Follow-up Study of Medication Refractory Essential Tremor Subjects Treated with ExAblate Neuro Thalamotomy in Clinical Trials**

The Objective of this observational follow-up study is to collect long-term information regarding the Safety and Efficacy of medication-refractory Essential Tremor subjects treated with the ExAblate Neuro System under P150038 (original IDE# G120246).

The Indications for Use claim for this system is as follows:

The ExAblate Neuro is intended for use in the unilateral Thalamotomy treatment of idiopathic Essential Tremor patients with medication-refractory tremor. Patients must be at least age 22. The designated area in the brain responsible for the movement disorder symptoms (*ventralis intermedius*) must be identified and accessible for targeted thermal ablation by the ExAblate device.

## 1. BACKGROUND and SIGNIFICANCE

### 1.1 Movement Disorder in Essential Disorders Patients

Essential tremor is the most common movement disorder with an estimated prevalence between 0.3% and 5.6% [1-5]. Recent epidemiological reports indicate that prevalence across 19 countries (pooled) was 0.9%, but increased to 4.6% among those 65 years and as high as 21.7% in those aged 95 and older. The condition is a genetically inherited disorder with a child of an ET person having a 50% chance of inheriting a gene causing the condition. Approximately 50-70% of people diagnosed with ET have a positive family history for the condition. Caucasians are 5 times more likely to report physician diagnoses of ET than are African Americans; Hispanics have a rate between them. Gender predisposition as reported in various articles is variable depending upon the author's population.

ET is a slowly progressive neurological disorder characterized by a tremor of the arms or hands that occurs during voluntary movements (intention tremor), such as eating/drinking and writing. The tremor may also present in the head (neck) and jaw and may affect voice. The disease may present in the teens or in the 40-50 age range. Generally, tremor begins in the arms and then spreads to these other regions in selected patients. Other types of tremor may also present, including postural tremor of the outstretched arms, and intentional tremor (below 5 Hz) and rest tremor of the arms. The amplitude of an intention tremor increases as an extremity approaches the endpoint of deliberate and visually guided movement (hence the name intention tremor). An intention tremor is usually perpendicular to the direction of movement. An intention tremor causes the person to overshoot or undershoot their target (dysmetria).

### 1.2 ExAblate Neuro System.

The non-invasive high-intensity focused ultrasound has been coupled with high resolution MRI to provide precise, consistent treatments that can be monitored in real-time. The development of phased array transducers allows for tightly focused treatment volumes and for the ability to compensate for distortions by tissue heterogeneity [6-8]. The landmark advance in the ExAblate transcranial MR guided focused ultrasound for neurosurgeons occurred as the ability to sonicate through the intact cranium was achieved with phased array transducers and acoustic modeling using CT reconstructions of the skull [6-10]. By coupling focused ultrasound technology with MRI, the ExAblate system allows detailed treatment plans to be performed and real time intra-procedure monitoring [11]. Standard MR sequences have been shown to reliably predict tissue damage during thermal lesioning with ultrasound [11, 12]. We anticipate that the ExAblate Neuro non-invasive thermal lesioning is safe and will provide several years of benefit through

---

 [http://www.medmerits.com/index.php/article/epidemiology\\_of\\_movement\\_disorders/P4](http://www.medmerits.com/index.php/article/epidemiology_of_movement_disorders/P4)

reduction of contralateral motor symptoms and potential medication side effects in ET subjects.

## **2 OBJECTIVES**

The objective of this clinical trial is to follow, observationally, the medication-refractory Essential Tremor subjects who underwent ExAblate Neuro thalamotomy under IDE# G120246 to capture long-term safety and effectiveness out to Year 5.

**Safety:** To evaluate long-term incidence and severity of adverse events (AE/AEs) associated with ExAblate Neuro treatment of medication-refractory ET

**Effectiveness:** To collect long term effectiveness and quality of life of the ExAblate Neuro treatment of medication-refractory Essential Tremor (ET).

This study is designed as a long-term prospective, observational clinical trial to follow device related safety, and long term effectiveness (CRST) and quality of life (QUEST) for subjects previously treated with ExAblate Neuro under IDE#120246.

The purpose of this protocol is to set the follow-up schedule for all IDE #G120246 subjects out to Year 5 in compliance with the post approval conditions.

### **2.1 Primary Endpoints**

#### **2.1.1 Safety**

*Safety of ExAblate will be determined by an evaluation of the incidence and severity of device / treatment related complications from the treatment day visit through ALL study follow ups through Year 5. Adverse events (type, frequency, severity) are expected to be similar to those of previous studies using ExAblate Neuro for Thalamotomy*

Recorded adverse events will be reported and categorized by investigators as definitely, probably, possibly, or unrelated to the device or procedure. Events which are not considered to be possibly or probably caused by the device are not required to be reported here.

#### **2.1.2 Effectiveness**

Primary effectiveness will be assessed using the CRST as scored by the site neurologist.

Secondary effectiveness will be followed using the QUEST quality of life patient outcomes questionnaire.

#### **2.1.2.1 Efficacy Assessments**

Tremor symptom severity will be assessed using the CRST as scored by the site neurologist at each follow-up visit. The CRST is a validated clinical instrument used to assess tremor symptom severity.

Quality of life will be evaluated using the QUEST assessment to assess durability (as measured by QUEST upper arm extremity questions) of the procedure. The QUEST is an ET specific assessment of quality of life changes associated with ET. Tröster *et al.*, 2005, developed QUEST as a clinical tool for correlating changes in 30 aspects of tremor severity, social and personal disability, and perception of health. An independent validation study of the QUEST performed by Martinez-Martin *et al.* concluded that most of the psychometric parameters were found to be satisfactory in their ability to assess the impact of ET on the patients' quality of life.

## **2.2 Study Hypothesis**

The purpose of this study is to continue to follow the ExAblate-treated medication-refractory ET subjects for long-term safety and effectiveness of MRI-guided focused ultrasound thalamotomy out through 5 years.

## **2.3 Case Report Form Data**

The study data will be collected electronically. This electronic data capture (EDC) system complies with the current guidance of 21 CFR Part 11, Electronic Records and Signatures.

# **3 DESCRIPTION OF PATIENT POPULATION**

## **3.1 Patient Selection**

### **3.1.1 Inclusion Criteria**

1. Subjects who have been treated with ExAblate thalamotomy for medication-refractory ET under previous clinical trials.

### **3.1.2 Exclusion Criteria**

1. Subjects who have had a subsequent intervention for ET on their treated side.

# **4 INVESTIGATIONAL PLAN**

The IRBs will be notified of the Post-Approval condition to follow these subjects and the study will be converted from IDE#120046 to a Post-Approval Study status under P150038. The study data will be collected electronically.

## **4.1 LTF Follow Up Periods Years 2 – 5 Post Treatment**

The treatment long term safety and effectiveness follow up will be completed annually from Year 2 through Year 5 post treatment under this protocol. It should be noted that at these visits, the CRST assessments will be performed and scored by the site neurologist.

The following evaluations should be performed at Year 2, Year 3, Year 4 and Year 5:

- Review of medications
- Physical exam
- CRST – Assessed by site evaluator
- QUEST questionnaire should be completed by the subject
- Adverse events

#### **4.2 Exit from the study for reason of alternative treatment**

In this study, subjects who opt for alternative treatments for Essential Tremor (not including medication change) at any point in the follow-up period will be exited from the study after completing the required study examinations. The last set of evaluations prior to alternative therapy is considered the last study visit. The reason(s) for study exit will be noted on the Case Report Forms. No analyses of post alternative treatment changes are planned.

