#### **4.3 Study Requirements and Visit Schedule**

All subjects who were part of the original IDE, IDE # G120246 in either the ET002 pivotal trial, or the ET002CA (Note: inclusive of all patients treated under the original Pivotal Study, those treated under the Continued Access approval, and those treated as part of the 1.5T Coil cohort) will be rolled into this PAS study at whatever stage of follow-up is coming due. Follow-up will be continuous from the time of treatment to the Year 5 visit.

Subjects who have not attained Month 12 will continue their schedule of visits as (originally scheduled):

- 1 Week  $\pm$  3 days
- 1 Month  $\pm$  7 days,
- 3 Month  $\pm$  14 days
- 6 Months  $\pm$  21 days
- 12 Months  $\pm$  4 month

| Table Error! No text of specified style in document.—1
Summary of Study Schedules and Measurements |                  |                             |                  |              |               |                |                |                |                 |
|---|------------------|-----------------------------|------------------|--------------|---------------|----------------|----------------|----------------|-----------------|
|   | Screening | Baseline Assessment* | Treatment | 1 Day | 1 Week | 1 Month | 3 Month | 6 Month | 12 Month |
| Consent  | X                |                             |                  |              |               |                |                |                |                 |
| Eligibility Evaluation with labs   | X                | X                           |                  |              |               |                |                |                |                 |
| Medications  | X                | X                           | X                | X            | X             | X              | X              | X              | X               |
| 30 day meds stabilization  |                  | X                           |                  |              |               |                |                |                |                 |
| Medical History  | X                |                             |                  |              |               |                |                |                |                 |

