### **5.5 Statistical Considerations and Sample Size**

There is no statistical consideration or sample size for this study. All ExAblate treated subjects who were treated under ET002 or ET002-CA will be included in this study, starting at the next scheduled study visit date; ET002-CA was FDA approved under IDE Supplement G120246/S07.

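### If the entry exclusion and the exit rule are followed as written, the Year 5 observed-data result omits re-treated subjects, and the document does not commit to reporting re-treatment

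*Combined protocol and SAP*

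**What the plan says.** **Who is in the study.** Section 5.5 states that "All ExAblate treated subjects who were treated under ET002 or ET002-CA will be included in this study". Section 4.3 agrees: treated subjects "will be rolled into this PAS study at whatever stage of follow-up is coming due", and besides the pivotal trial it names "those treated under the Continued Access approval, and those treated as part of the 1.5T Coil cohort". Section 3.1.2 has a single exclusion: "Subjects who have had a subsequent intervention for ET on their treated side".

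**What happens on alternative treatment.** Section 4.2 states that "subjects who opt for alternative treatments for Essential Tremor (not including medication change) at any point in the follow-up period will be exited". Exit follows the examinations that are due. It adds: "The last set of evaluations prior to alternative therapy is considered the last study visit", and "No analyses of post alternative treatment changes are planned". The rule has no side limit. Section 7.1 lists the same event among the grounds on which the investigator has discretion to withdraw a subject.

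**What is recorded.** Section 4.2 has the exit reason entered on the case report form, and Table 4.2-2 schedules an Exit Form at each of Years 2 to 5.

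**What is analysed.** Section 5.6 plans an observed-data analysis and an LOCF analysis, and says that ET002 and ET002-CA data will be used alongside the data collected here. Section 5.7 adopts the pivotal study's SAP, restricted to site-assessor data. That SAP is not part of the document.

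**The concern.** Section 6 asks whether the improvement in the composite score lasts to 5 years in the patients who were treated, and sections 2 and 8 set the same population. It also expects that some patients will lose their improvement. A further procedure on the treated side is a plausible sign of that loss, yet it is the event that ends a subject's data or, under section 3.1.2, may keep the subject out altogether.

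If such subjects leave the analysis and their number is not shown beside it, a reader of the Year 5 result cannot tell how far it depends on who remained. The conflicting entry and exit wording adds to this, because sites could apply the rules differently and so change who contributes data.

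**Working it through.** **Step 1: two conflicts in the text.**
- Entry: section 3.1.2 removes subjects with an earlier treated-side intervention; sections 4.3 and 5.5 include all treated subjects. Subjects roll in at different stages, so re-treatment before roll-in is possible.
- Exit: section 4.2 makes exit automatic; section 7.1 makes withdrawal for the same event discretionary.

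**Step 2: what each analysis would contain, with sections 3.1.2 and 4.2 followed as written.**

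| Subject | Observed data, Year 5 | LOCF, Year 5 |
|---|---|---|
| Not re-treated, attends Year 5 | Own score | Own score |
| Enrolled, then treated-side procedure | None | Last pre-therapy score |
| Enrolled, then other-side treatment | None | Last pre-therapy score |
| Treated-side procedure before roll-in | None | None |

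If sections 4.3 and 5.5 govern instead, subjects in the last row are in the study, but the document does not say how their scores are handled.

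**Step 3: size, for illustration only.** The document gives no re-treatment rate and no sample size, so there is no planned figure to reproduce.

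Inputs:
- R, mean improvement in retained subjects: 39.6%, the Month 12 ExAblate ITT value for the composite in the section 8 table (N=56). That it holds at Year 5 is assumed. Section 5.7 limits this study to site-assessor scores, and the section 8 table does not state its scoring source.
- q, proportion with treated-side re-treatment: assumed 5%, 10% or 20%.
- Re-treated subjects coded 0% improvement: assumed.

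All-treated mean = (1 − q) × R. Observed-data mean = R. Gap = q × R.

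| q | All-treated mean | Gap |
|---|---|---|
| 5% | 0.95 × 39.6 = 37.62 | 1.98 |
| 10% | 0.90 × 39.6 = 35.64 | 3.96 |
| 20% | 0.80 × 39.6 = 31.68 | 7.92 |

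For scale, the half-width of the Month 12 interval is (45.3 − 34.0) / 2 = 5.65 points.

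**Step 4: LOCF against the same 0% coding.** If all re-treated subjects are enrolled exits whose last score before therapy averages L, the gap is q × L. With L assumed to be 20%, it runs from 0.05 × 20 = 1.0 to 0.20 × 20 = 4.0 points. If all of them were excluded at entry, LOCF has nothing to carry forward and its gap equals the observed-data gap.

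**Step 5: direction.** If the omitted subjects would really have averaged m, the gap is q × (R − m). It is positive for m below 39.6%, zero at 39.6% and negative above it. A low m is plausible for treated-side re-treatment. For subjects who exit to have the other side treated, m could fall on either side of R.

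No head counts are given, because section 4.3 adds the Continued Access and 1.5T Coil cohorts to the pivotal 56 without stating a total.

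**The case against.** The strongest case for the plan has five parts.

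- **Direction.** A reader might infer that the retained subjects are a selectively favourable group and the Year 5 mean is biased upward. The document does not support that as a general statement. The procedure is unilateral and section 4.2 has no side limit, so a subject with a good result who seeks treatment for the other side also exits, and losing such subjects could lower the observed mean. This stands; only treated-side re-treatment has a likely direction.
- **Capture.** A reader might infer that re-treatment goes unrecorded. It does not for enrolled subjects: the exit reason and Exit Form are both in the plan. This stands; the gap is in reporting. Subjects excluded at entry may have no such form, and the document does not say that side is recorded.
- **The pivotal SAP.** It may already contain disposition tables or a failure rule. This cannot be checked here, so the statement is limited to what the document shows.
- **LOCF.** It retains enrolled exits. That helps only as far as decline was recorded before exit, at visits a year apart with windows of ±4 months, and it does nothing for subjects excluded at entry.
- **Observational design.** There is no formal hypothesis, and stopping effectiveness data at alternative therapy is prespecified. Scores after another procedure are confounded, so leaving them unanalysed is reasonable. That does not explain leaving the event itself uncounted.

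**Conclusion.** The point holds in a limited form and should be fixed. Sections 3.1.2, 4.3 and 5.5 conflict on entry, and sections 4.2 and 7.1 on exit. If sections 3.1.2 and 4.2 are followed as written, the observed-data Year 5 result omits re-treated subjects, and LOCF omits those excluded at entry. Nothing in the document commits to reporting re-interventions or counting them against durability.

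For treated-side re-treatment the omission is likely to favour durability; the net effect with other-side exits included cannot be derived in size or direction. The 2.0-7.9 point range is distance from a deliberately strict coding, not an estimate of bias. It rests on an assumed re-treatment rate of 5-20%, the 0% coding, and the Month 12 mean of 39.6% persisting to Year 5. The reporting gap does not depend on those assumptions.

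**What to change.** 1. Reconcile sections 3.1.2, 4.2, 4.3, 5.5 and 7.1 on the analysis set, so that every ExAblate-treated subject is in the denominator for the LOCF and sensitivity analyses. Use the ET002 and ET002-CA data, as section 5.6 allows, for those re-treated before roll-in. This will not alter the observed-data mean, since exited subjects have no later values. It changes the analysis set and leaves clinical management as it is.
2. Tabulate re-interventions by side and timing, up to study exit, beside the observed-data and LOCF results. Take them from the existing exit records, and from ET002 and ET002-CA records for those re-treated before roll-in. Add a side field to the Exit Form if it has none.
3. Add one sensitivity analysis that codes treated-side re-intervention as non-sustained benefit (0% improvement from its date). Label it a conservative bound, because a re-treated subject may keep some benefit and section 1.1 describes ET as progressive. Treat other-side exits as censored, not as failures.

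If the pivotal SAP already has such rules, restate them in this protocol.

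The cost is revised wording, a little more analysis and possibly one form field. Reported durability may look less favourable.

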#### **4.3 Study Requirements and Visit Schedule**

All subjects who were part of the original IDE, IDE # G120246 in either the ET002 pivotal trial, or the ET002CA (Note: inclusive of all patients treated under the original Pivotal Study, those treated under the Continued Access approval, and those treated as part of the 1.5T Coil cohort) will be rolled into this PAS study at whatever stage of follow-up is coming due. Follow-up will be continuous from the time of treatment to the Year 5 visit.

Subjects who have not attained Month 12 will continue their schedule of visits as (originally scheduled):

- 1 Week  $\pm$  3 days
- 1 Month  $\pm$  7 days,
- 3 Month  $\pm$  14 days
- 6 Months  $\pm$  21 days
- 12 Months  $\pm$  4 month

| Table Error! No text of specified style in document.—1
Summary of Study Schedules and Measurements |                  |                             |                  |              |               |                |                |                |                 |
|---|------------------|-----------------------------|------------------|--------------|---------------|----------------|----------------|----------------|-----------------|
|   | Screening | Baseline Assessment* | Treatment | 1 Day | 1 Week | 1 Month | 3 Month | 6 Month | 12 Month |
| Consent  | X                |                             |                  |              |               |                |                |                |                 |
| Eligibility Evaluation with labs   | X                | X                           |                  |              |               |                |                |                |                 |
| Medications  | X                | X                           | X                | X            | X             | X              | X              | X              | X               |
| 30 day meds stabilization  |                  | X                           |                  |              |               |                |                |                |                 |
| Medical History  | X                |                             |                  |              |               |                |                |                |                 |
| Physical Exam  | X                | X                           |                  | X            | X             | X              | X              | X              | X               |
| Neurological status  | X                |                             | X                | X            | X             | X              | X              | X              | X               |
| CRST   | X                |                             |                  |              |               | X              | X              | X              | X               |
| QOL (QUEST)  | X                | X                           |                  |              |               | X              | X              | X              | X               |
| PHQ-9  | X                |                             |                  |              |               | X              | X              | X              | X               |
| CT   | X                |                             |                  |              |               |                |                |                |                 |
| MR   |                  | X                           | X                |              |               |                |                |                | X               |
| Treatment  |                  |                             | X                |              |               |                |                |                |                 |
| Adverse Events   |                  |                             | X                | X            | X             | X              | X              | X              | X               |
| Forms "UB-04 (In Patient subjects) or CMS-1500 (Out Patient subjects)   |                  | X                           | X                | X            | X             | X              | X              | X              | X               |
| Exit Form  |                  |                             |                  |              |               |                |                |                | X               |

The table below summarizes the long-term study visit schedule and procedures.

The study visits are as follows:

Year 2 ± 4 Month;

Year 3 ± 4 Month,

Year 4 ± 4 Month,

Year 5 ± 4 Month.

